### **Aim 2: Determine independent factors associated with ASE and ACE concordance.**

Hypothesis: We postulate that practicing the ASE or ACE between visits will be associated with concordance between the ASE/ACE and DARE at Visit 2.

Objective: Using regression analysis, determine factors associated with ASE and ACE concordance.

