### **Aim 2**

There is one primary outcome for Aim 2: the association between practice and concordance at Visit 2. Concordance is binary and equals 1 when both participant and clinician identify an abnormality or agree on its absence; thus, the statistical analysis is premised on detecting an anal abnormality, not a cancer. We postulate that practicing the ASE or ACE between visits will be associated with ASE/ACE and DARE concordance at Visit 2. To derive unbiased estimates in multivariable modeling for the association between practice and concordance, we will use directed acyclic graphs to identify potential confounders to include in models (e.g., age, ethnicity, race, city, anxiety, chronic disease, and, for ACE, co-teaching and reported familiarity with a companion’s body) and intermediate variables to exclude from multivariate modeling; however, given successful randomization, bias, including confounding, should be minimized. Both intent-to-treat and per-protocol analyses will be conducted (we expect a similar proportion of persons in the practice and non-practice arms to switch arms of their own accord, i.e., crossover, between visits). The association will be assessed with logistic regression. After univariate analyses, variables where  $p \leq 0.25$ , and which are not intermediate variables, will be added to a multivariable model using backward selection with binary practice (yes/no) retained in the model. After adjustment for potential confounders, factors where  $p < 0.05$  (two-sided) will be considered statistically significant. Adjusted and un-adjusted odds ratios will be reported with 95% confidence intervals. We will use a similar approach to derive unbiased estimates in multivariable modeling for the association between continuous waist size and concordance; however, we will also use ROC curves to ascertain the potential for a threshold effect of waist circumference size on concordance. We will also assess the full set of other study data and their potential associations with concordance. For multiple comparisons we will use the False Discovery Rate. Finally, we will investigate effect modification by age and individual/couple status.

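### Aim 2 picks confounders by causal graph and then lets p-values drop them, and it does not say which tests the False Discovery Rate covers

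*Combined protocol and SAP*

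**What the plan says.** The objective listed under Aims for Aim 2 is broad: "Using regression analysis, determine factors associated with ASE and ACE concordance". The Aim 2 part of Statistical Analysis is narrower about what is primary: "There is one primary outcome for Aim 2: the association between practice and concordance at Visit 2".

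That section gives two rules for choosing covariates:

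- By subject matter: "we will use directed acyclic graphs to identify potential confounders to include in models". The graphs also serve to identify intermediate variables, which are left out.
- By p-value: variables with univariate p≤0.25, "and which are not intermediate variables", "will be added to a multivariable model using backward selection with binary practice (yes/no) retained in the model". Factors with two-sided p<0.05 after adjustment are then called significant, and odds ratios are reported with 95% intervals.

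Continuous waist size is to be analysed in much the same way. Both intent-to-treat and per-protocol analyses of practice are planned, with crossover between arms expected.

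Two further sentences follow. One widens the search: "We will also assess the full set of other study data and their potential associations with concordance". The next reads: "For multiple comparisons we will use the False Discovery Rate". Neither gives a candidate list, a model, the set of tests covered or the rate to be controlled.

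**The concern.** A variable chosen from a causal graph is in the model because leaving it out would bias the estimate, whatever its p-value in this sample. Under the second rule, the same variable is removed if it misses p≤0.25 on its own or loses out in backward selection. Only practice is exempt. The plan does not say which rule prevails.

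This matters most where randomisation gives no protection. Waist size is not randomised. In the per-protocol analysis, actual practice is partly self-selected. In both, a discarded confounder biases the odds ratio, and an interval computed as if the final model had been fixed in advance does not allow for the selection.

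The second matter is the search for other factors. If the False Discovery Rate is applied only to variables that have already survived a 5% cut, it corrects nothing. The plan leaves that reading open.

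**Working it through.** **Inputs from the documents.** The Aim 2 sample size is 800−44=756, then 756−76=680, which reproduces. At the planning concordance of 85%, 680×0.15=102 results are discordant. At the pilot figure of 93% (Background), 680×0.07≈48 are. The plan states no error rate for the factor search, so there is no figure of its own to reproduce on this point.

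**Assumed, because the plan is silent.** A stay level of 0.05 in backward selection, waist kept in its own model as practice is in its model, the Benjamini-Hochberg procedure at q=0.05, and the number of candidates m.

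**1. How easily one real confounder is lost.** For a continuous variable with odds ratio 1.3 per SD (assumed), the chance of reaching p<0.05 is about Φ(√(n·p(1−p))·ln 1.3 − 1.96).

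- At 85%: √(680×0.1275)×0.262−1.96 = 0.48, so Φ≈0.69.
- At 93%: √(680×0.0651)×0.262−1.96 = −0.21, so Φ≈0.42.

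Simulation gave 69% and 43%. A confounder of this strength would therefore fail the 5% level roughly 31% or 57% of the time.

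**2. What that does to the waist interval.** Illustration with n=680, six mutually independent confounders each of odds ratio 1.3 per SD and each correlated 0.25 with waist, and no true waist effect. The p≤0.25 screen and backward selection are applied with waist retained.

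| Concordance | Coverage after screen and selection | Coverage with all six kept |
|---|---|---|
| 85% | about 69% | 95% |
| 93% | about 65% | 95% |

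A null waist effect would thus be declared real about 31% or 35% of the time (100−69, 100−65), against the nominal 5%.

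**3. The False Discovery Rate on survivors only.** Suppose k factors survive, all with p<0.05. Benjamini-Hochberg keeps all k if the largest p is at most (k/k)×q = 0.05. It always is, so nothing is removed.

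**4. Chance of at least one false factor when no candidate is real.** With independent tests at 5% this is 1−0.95^m. The simulations used n=680 and 85% concordance.

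| Assumed m | 1−0.95^m | Screen and selection, rate applied to survivors | Rate applied to all candidates |
|---|---|---|---|
| 10 | 40% | 38-42% | about 5% |
| 20 | 64% | 61-64% | about 4% |
| 40 | 87% | 86-88% | about 5% |

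The expected number of false factors on the survivors-only reading is about 0.05×m. A correlation of 0.3 among candidates does not help: 65% at m=20 and 89% at m=40.

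**5. The practice test.** In the same simulations, with arm assigned at random and forced into the model, the type I error for practice was about 4-6%.

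**The case against.** The case for the plan has real weight.

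- The screen and backward selection are described for the practice association and carried over to waist size. The sentence on the other study data names no method. A reader might infer that the selection runs over the whole data set, but the text does not say so.
- The False Discovery Rate sentence comes directly after the sentence on the other data. Reading it as covering all those candidates is natural, and the chance of a false factor is then about 5%. A reader might infer that spurious factors are very likely to be reported. That needs the other reading and an assumed candidate count. For the eight confounders named as examples, the survivors-only figure is 33%.
- That the correction removes nothing depends on the assumed stay level and q, and on a family made up only of selected factors. If practice is counted in the family, 88% at 40 candidates falls to 62%.
- The survey instruments are not reproduced, so candidates cannot be counted. Answers to the Visit 2 post-exam survey come after the clinician's result is disclosed and are poor candidates anyway.
- The graph and the screen agree on leaving out intermediate variables.

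All of this stands. It limits the multiplicity part to a conditional statement about an undefined family. It does not reconcile the two confounder rules: no sentence says that graph-chosen confounders survive the p-value steps, and only practice is exempted.

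**Conclusion.** The firm finding is the conflict between the two confounder rules, which does not depend on any candidate count. As written, p-values can remove the confounders that the graphs select. The waist-size and per-protocol practice results would then carry bias and intervals that ignore the selection.

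The coverage of about 69% or 65% shows that the loss can be large, but it is not a forecast. It rests on six moderate confounders all acting in the same direction. Fewer, weaker or opposing confounders would cost less.

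The False Discovery Rate finding is conditional. The plan does not define the family. One permitted reading gives about 5%; the other gives about 40%, 60-64% and 86-88% at an assumed 10, 20 and 40 candidates.

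A reader might also infer that the primary Aim 2 result is unsound. The calculations do not support that for the intent-to-treat comparison, because practice is randomised and forced into the model. The point should be corrected in the analysis plan, but it does not threaten the primary test.

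**What to change.** Delete the p≤0.25 screen and the backward selection.

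- For practice and for waist size, fit one model each, with the graph-chosen confounders listed in advance and always kept.
- For the other study data, list the candidates and state the model that yields each p-value. Apply the False Discovery Rate at a stated q to the p-values of all candidates before any selection. Say that this rule, rather than unadjusted p<0.05, decides which factors are declared.
- Label that search exploratory.

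The cost is a change of wording and slightly different code. The downside is that fewer factors will be declared.

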## **SAMPLE SIZE**

800 participants completing Visit 1: 400 in Chicago and 400 in Houston

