### **Visit 1 Overview**

With identical protocols in Houston and Chicago, persons will receive a short didactic presentation on anal anatomy, practice on pelvic mannequins, and get instructions on doing an ASE or ACE (figure 1). The clinician will then swab the anal canal of each participant, and perform a DARE, without disclosing the results, before leaving participants in private to perform their ASE or ACE. Participants will record their results (as either "normal" or "abnormal") and then get the clinician's DARE result along with any needed referrals; thus, the participant result will be judged against the clinician gold standard. Participants will then complete the post-exam computer-assisted self-interview. At the end of Visit 1, persons will be randomized to a condition of encouraged practice of the ASE (or ACE) or a condition of neither encouragement nor discouragement from practice. Persons will have Visit 2 in 6 months when concordance of self- and companion exam with a clinician DARE will again be assessed. Data collected during these visits will be analyzed to complete the aims.

Figure 1.

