## STATISTICAL ANALYSIS

### Aim 1

The central hypothesis is that both ASE and ACE at Visit 1 will have  $\geq 70\%$  sensitivity and  $\geq 90\%$  specificity using the clinician DARE as the gold standard. We will test our central hypotheses at Visit 1 by comparing ASE and ACE sensitivity and specificity to random guessing (i.e., sensitivity and specificity=50%) using a one-sample test for proportion. We will then conduct a test of equivalence using two, one-sided likelihood score tests to compare ASE sensitivity in Houston vs Chicago clinics to determine if the ASE performance is equivalent in each city; thus, we will assess the homogeneity of Houston and Chicago sensitivity before combining results. We focus on sensitivity since this factor performed worse than specificity in the pilot study and had wide confidence limits. Sensitivity will also be stratified by other factors, for example location (anal canal vs perianal) and co-morbidities, to determine the effect on sensitivity. Tests will be two-sided with a 0.05 alpha. We will estimate percent agreement, positive predictive value, negative predictive value and perform receiver operating characteristic (ROC) curve analysis for a binary outcome.

To test our central hypothesis, our pilot data indicate 1) 11% of persons will have condyloma, hemorrhoids, skin tags, scars, or malignant tumors at Visit 1 at the anal canal or perianal region, and 2) a sensitivity of  $\geq 70\%$  on ASE and 78% on ACE and specificity  $\geq 90\%$  for both at Visit 1. Given a null value for sensitivity and specificity of 50% (since we seek to rule out accuracy due only to chance), our power to detect sensitivity  $\geq 70\%$  among 600 individuals is 0.90 and 0.81 among 200 couples. Power to detect specificity  $\geq 90\%$  among both individuals and couples is  $>0.90$ . For multiple comparisons we will use the False Discovery Rate. Using a test of equivalence, our hypothesis of no difference in ASE sensitivity between Houston and Chicago assumes that a difference of less than 0.15 constitutes equivalent sensitivity given that a smaller difference may have little practical relevance for adjusting the protocol in either city. Under this definition of equivalence, we have at least 0.87 power to detect a lack of equivalence in sensitivity between the cities if the actual observed difference ranges from 0 to 0.05. Power was assessed with PASS13.

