For the Aim 2 hypothesis, that practice will be associated with concordance in all persons at Visit 2, sample size will be adjusted downward by dropouts and non-resolving abnormalities from Visit 1. We expect 11% of persons ( $n=88$ ) to have an abnormality at Visit 1 (based on pilot data) with most of these being hemorrhoids and condyloma. We conservatively expect 50% of hemorrhoids and condyloma to resolve in 9 months; thus, there will be a minimum of 44 non-resolving events from Visit 1 and another 10% of persons will dropout ( $800-44=756$ ;  $756-76=680$ ). We have 80% power to detect an odds ratio of at least 1.55 or larger if concordance is 85% and  $n=680$ .

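### The Aim 2 analysis size of 680 rests on a 9-month resolution rate applied to every abnormality, which does not match the 6-month Visit 2 or the case mix; the detectable odds ratio needs restating whichever n is used

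*Combined protocol and SAP*

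**What the plan says.** The Sample Size section sets the starting number: "800 participants completing Visit 1: 400 in Chicago and 400 in Houston". The Aim 2 part of Statistical Analysis then reduces it. The abnormality count is given as "We expect 11% of persons ( $n=88$ ) to have an abnormality", "with most of these being hemorrhoids and condyloma". The resolution step is "We conservatively expect 50% of hemorrhoids and condyloma to resolve in 9 months; thus, there will be a minimum of 44 non-resolving events". Those 44 are subtracted, 10% of the remaining 756 are taken as dropouts, and 680 is left. The power statement for the single primary outcome of Aim 2 uses that figure: 80% power for an odds ratio of 1.55 with concordance at 85%.

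Elsewhere the interval is different. Visit 1 Overview says "Persons will have Visit 2 in 6 months". Preparation for Visit 2 schedules contact around the six-month anniversary, and Duration of Participant Activities gives six months. The change history records that version 3.8 moved the interval to six months.

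The Aim 1 text lists what the 11% contains: "11% of persons will have condyloma, hemorrhoids, skin tags, scars, or malignant tumors at Visit 1". No resolution rate is given for skin tags, scars or malignant tumors.

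**The concern.** Three features of the resolution step do not fit the rest of the protocol.

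- **Interval.** The rate is for 9 months, but the outcome is assessed at 6 months. This is current statistical text, not an entry in the change log.
- **Base.** A rate stated for a subset, described only as most of the abnormalities, is applied to all 88.
- **Wording.** The sentence calls the 50% conservative, which implies that the loss may be smaller than 44. It then calls 44 a minimum, which implies that the loss may be larger. It cannot be both, and 44 is used as the planning value.

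There is also an open question about the analysis set. The hypothesis is worded for everyone seen at Visit 2, an intent-to-treat analysis is planned, and all participants are asked back whatever their earlier result. Yet the sample-size text removes people whose abnormality has not resolved, which is known only after randomization.

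At stake is the only analysis size given for the primary Aim 2 comparison, and the effect that the trial says it can detect.

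**Working it through.** **1. The plan's own figure.** 800 × 0.11 = 88; 88 × 0.50 = 44; 800 − 44 = 756; 756 × 0.10 = 75.6, rounded to 76; 756 − 76 = 680. It reproduces exactly.

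**2. Correcting interval and base.** Let s be the share of the 88 that are hemorrhoids or condyloma and r the proportion of those resolved by 6 months. Other abnormalities are assumed not to resolve. Then

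n = (800 − 88 × (1 − s × r)) × 0.90.

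Neither s nor r is in the documents, so both are assumptions. For r, scaling 50% at 9 months gives 0.50 × 6/9 = 0.333 (linear) or 1 − 0.5^(6/9) = 0.370 (constant hazard). For s, the word most is read as 51% to 90%.

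| Case | Non-resolving | n | Change from 680 |
|---|---|---|---|
| s = 90%, constant hazard | 58.7 | 667 | −1.9% |
| s = 90%, linear | 61.6 | 665 | −2.2% |
| s = 51%, constant hazard | 71.4 | 656 | −3.5% |
| s = 51%, linear | 73.0 | 654 | −3.8% |
| Nothing resolves | 88 | 641 | −5.7% |
| Nobody excluded (800 × 0.90) | – | 720 | +5.9% |

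**3. Effect on power and detectable odds ratio.** Inputs: 1:1 allocation (Randomization), two-sided alpha 0.05 and concordance of 85% (Aim 2). The plan does not say which arm has 85%, so both readings are shown. An odds ratio of 1.55 corresponds to 85.0% vs 89.8% if 85% is the lower arm, and to 78.5% vs 85.0% if it is the higher arm. The power formula is Φ[(|p1 − p2| − 1.96 × SE0)/SE1], with SE0 the pooled and SE1 the unpooled standard error for n/2 per arm.

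| n | Power at OR 1.55, 85% lower / higher | Detectable OR at 80% power, 85% lower / higher |
|---|---|---|
| 720 | 0.49 / 0.61 | 1.95 / 1.71 |
| 680 | 0.47 / 0.59 | 1.99 / 1.74 |
| 667 | 0.46 / 0.58 | 2.01 / 1.74 |
| 654 | 0.45 / 0.57 | 2.02 / 1.75 |
| 641 | 0.44 / 0.57 | 2.04 / 1.76 |

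Taking 85% as the average of the two arms gives power of 0.52 at n=680. A one-sided test gives 0.59 to 0.71, still short of 0.80. Treating practice as a continuous covariate, per standard deviation, gives 0.98, but practice is binary in the plan. Under the two-sided test, 80% power at an odds ratio of 1.55 needs about 1,114 participants in total (85% as higher arm) to 1,514 (lower arm).

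**The case against.** The strongest reply is that the 50% is described as conservative. If the authors believe that the true 9-month rate is higher, 680 may survive the move to 6 months. Under constant hazard, a 9-month rate of 1 − 0.5^(9/6) = 65% gives 50% at 6 months, and n stays at 680 if the rate applies to all 88, or 676 if it applies to 90% of them. The protocol also provides for treatment or referral of abnormalities found at Visit 1, so resolution may come early and differ little between 6 and 9 months. Linear or constant-hazard scaling is the reviewer's device, not the plan's.

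This stands. A reader might infer from "there will be a minimum of 44 non-resolving events from Visit 1" that 680 is a proven maximum, or that correcting the inputs can only reduce n. The documents do not support either: the conservative label in the same sentence points the other way, and keeping everyone in the analysis raises n to 720.

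A second reply is that the change in n is immaterial. On n alone that is fair: the detectable odds ratio barely moves. It does not rescue the stated 1.55, which is not reached at any n in the range.

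**Conclusion.** The inputs to 680 contradict the visit schedule and the plan's own description of the abnormalities, and the sentence that links them is internally inconsistent. The subtraction itself is correct.

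Under the stated assumptions the downward corrections take n to about 654 to 667, with a floor of 641. That is a fall of about 2% to 4%, at most 5.7%, and a loss of about 1 to 2.5 points of power. Whether n is in fact overstated cannot be settled from the documents, because they give no 6-month rate, no case mix and no clear analysis set.

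Nor should a reader conclude that the interval or the base explains the optimistic power statement. The stated 80% power for an odds ratio of 1.55 already fails at n=680, where power is about 0.47 to 0.59. For n from 641 to 720 the detectable odds ratio is about 1.71 to 1.76 if 85% is the higher arm and 1.95 to 2.04 if it is the lower. These figures rest on two equal arms, a two-sided 0.05 test and no covariate adjustment.

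**What to change.** In the Aim 2 sample-size text:

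1. Replace the 9-month interval with the 6-month one and state the resolution rate assumed for 6 months, with its source.
2. State the share of abnormalities that are hemorrhoids or condyloma, apply the rate only to that share, and say what is assumed for the rest. Drop either the conservative or the minimum label.
3. Say whether people with non-resolving abnormalities are in the intent-to-treat set (n=720) or excluded (about 641 to 667 under the assumptions above). If excluded, explain how that fits with intent to treat.
4. Say which arm the 85% refers to, and restate the detectable odds ratio for the chosen n in place of 1.55.

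The cost is a few sentences and one power calculation. No visit, procedure or data item changes. The sponsor has to make one decision, on the analysis set, and accept a larger detectable odds ratio than the one now stated.

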### **Randomization**

At the end of Visit 1, all participants will be randomized to one of two conditions: Arm 1 (practice) or Arm 2 (no practice). One-half of participants in each city will be randomly selected and encouraged to practice the ASE/ACE 3 months before Visit 2. Persons randomized to the control arm will neither be encouraged nor discouraged from practicing the ASE/ACE.

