#### **Arm 2 – Non-practice Arm**

Persons in the non-practice arm will be reminded that we will schedule a Visit 2 appointment and that we will also contact them periodically to keep in touch to support study retention. Persons in the non-practice arm will be neither encouraged to practice nor discouraged from practice. If asked about practice, study staff will reply that the participant is not expected to practice since the ASE/ACE is not known at this time to be beneficial. The PAC Palpation Study is trying to determine if it’s beneficial.

After end-of-Visit 1 study staff will provide a \$50 incentive and also tell the participants about the Referral Program for recruitment. Anticipated visit duration is about 75 and 90 minutes for individuals and couples, respectively.

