### **Between Visit 1 and Visit 2 study procedures**

#### Arm 1 – Practice.

*If participant had a normal DARE at Visit 1, OR if participant had an abnormal DARE at Visit 1 that required no referral (e.g., a scar or non-prolapsed hemorrhoids),* study staff will make reminder calls (or emails/texts) and follow-up calls for the scheduled practice session. At the follow-up calls, study staff will record the participant's result for the self/companion exam and the level of anxiety and pain, if any, associated with the exam. If the participant reports more than minimal pain and anxiety, they will be asked to return to the clinic for an HCP exam.

If a new abnormality is detected by the participant, i.e., an abnormality not recorded at Visit 1, the study coordinator will request they return to the study clinic site for a clinical examination. While requesting they return to the clinic, staff will record the participant description of the abnormality, and their level of anxiety and pain associated with the ASE/ACE practice. When the participant returns to the clinic, staff will record medical outcomes for each person.

Participants not wanting to return to the clinic will be provided referrals by the health care provider at the clinic. Efforts will be made to contact persons once each week for up to four weeks to encourage a return to the study clinic or completing of the referral elsewhere.

*If participant had an abnormal DARE at Visit 1 that required referral (e.g., condyloma or suspicious lesion),* the person can still participate in practice unless the clinician advises that the ASE/ACE is contraindicated due to the Visit 1 abnormality, or the person reported more than minimal anxiety or pain due to the ASE/ACE at Visit 1. During follow up, staff will ask about referral completion, resolution of the abnormality, and practice ASE/ACE results. If referral has still not been completed, staff will again encourage completion of referral or coming back to an upcoming study clinic for another DARE.

Participant activity and results between Visit 1 and Visit 2 will be documented in REDCap.

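### Aim 2 promises an intent-to-treat analysis of Visit 2 concordance but gives no method for the roughly 10% expected to have no Visit 2 outcome

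*Combined protocol and SAP*

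**What the plan says.** All references are to the combined protocol and SAP.

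- **Design.** The SAMPLE SIZE section plans "800 participants completing Visit 1: 400 in Chicago and 400 in Houston". Under Randomization, "One-half of participants in each city will be randomly selected and encouraged to practice the ASE/ACE 3 months before Visit 2".
- **Outcome.** Statistical Analysis, Aim 2, has one primary outcome: the association of practice with concordance at Visit 2. Concordance needs a participant result and a clinician DARE. Under Preparation for Visit 2 and Visit 2 Study Procedures, the first comes from a home exam in the 24 hours before the visit and the second from the clinic.
- **Analysis.** Aim 2 states that "Both intent-to-treat and per-protocol analyses will be conducted", using logistic regression. Covariates pass a univariate screen at p≤0.25 and then backward selection; only practice is forced to stay.
- **Sample size.** "sample size will be adjusted downward by dropouts and non-resolving abnormalities from Visit 1". The text adds that "there will be a minimum of 44 non-resolving events from Visit 1" and that "another 10% of persons will dropout", which leaves 680.
- **Contact between visits.** In the practice arm, for participants whose Visit 1 DARE was normal or needed no referral, "study staff will make reminder calls (or emails/texts) and follow-up calls for the scheduled practice session". A new abnormality, or more than minimal pain and anxiety, leads to a request to return to the clinic. In the non-practice arm, "we will also contact them periodically to keep in touch to support study retention". The practice arm is promised the same periodic contact. Under Preparation for Visit 2, both arms are contacted two weeks and two days before the visit.
- **Baseline.** Under Visit 1 Detail, the coordinator holds both the participant's and the clinician's Visit 1 results when randomising.

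**The concern.** A participant who does not reach Visit 2 has no concordance value. The plan defines no intent-to-treat population, missing-outcome rule, imputation, weighting or sensitivity analysis for missing outcomes; its text on attrition is about preventing it. Logistic regression omits records without an outcome, so the promised intent-to-treat comparison becomes, by default, a comparison of those who return.

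Randomisation balances the arms at the end of Visit 1, but it does not protect a comparison restricted to returners. The arms have different experiences between visits: the practice arm has extra contact, which may help retention, and extra tasks, which may harm it. If loss differs by arm and dropouts differ in concordance from those who stay, the practice odds ratio is biased. Equal loss does not guarantee safety either, if different kinds of people leave each arm.

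A baseline measure of the same outcome is available by design. Visit 1 concordance is not among the plan's named examples of confounders, and it could enter the practice model only by surviving the screening and selection steps.

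**Working it through.** **The plan's own figure.** 800 − 44 = 756; 10% of 756 = 75.6, taken as 76; 756 − 76 = 680. This reproduces. Split equally, that is 340 completers and 38 dropouts per arm.

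**Yardstick.** The plan's target is an odds ratio of 1.55 with 85% concordance. From 85%, the odds are 0.85/0.15 = 5.667; × 1.55 = 8.783; 8.783/9.783 = 89.8%. The difference is 4.8 points, or about 16 people per 340. The 38 expected missing per arm exceed that. I use the target only as a scale; whether 680 people give 80% power is a separate question.

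**Standard error** of the difference: √(2 × 0.85 × 0.15 / 340) = 2.7 points.

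**Bias with no true effect.** Assume true concordance of 85% in both arms, loss d and dropout concordance q. The completer rate is (0.85 − d·q)/(1 − d). The documents give neither d by arm nor q, so both are assumed. Practice minus control:

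| Dropout concordance q | Loss 5% practice, 15% control | Bias | In SEs | Bias at 7% vs 13% |
|---|---|---|---|---|
| 81% | 85.2% vs 85.7% | −0.5 points | 0.2 | −0.3 |
| 75% | 85.5% vs 86.8% | −1.2 points | 0.45 | −0.7 |
| 65% | 86.1% vs 88.5% | −2.5 points | 0.9 | −1.5 |

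Swapping the loss rates reverses every sign. As odds ratios, the 75% and 65% rows at 5% vs 15% are 0.90 and 0.80, or 1.11 and 1.25 when reversed. With equal loss and equal q, the bias is zero. With 10% loss in each arm but q = 65% in practice and 85% in control, completers show 87.2% vs 85.0% (odds ratio 1.21).

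**Which q is plausible?** The table of participant time burden expects 28 discordant results per city at Visit 1: 56/800 = 7%. Assume Visit 1-discordant people drop out at three times the rate of others and half are concordant at Visit 2.

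- Dropout rate of the others: 0.10/(0.93 + 3 × 0.07) = 0.10/1.14 = 8.8%; of the discordant, 26.3%.
- Discordant share of dropouts: 0.21/1.14 = 18.4%.
- Visit 2 concordance of the others: (0.85 − 0.07 × 0.5)/0.93 = 87.6%.
- q = 0.184 × 0.5 + 0.816 × 0.876 = 81%.

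To reach 75% at threefold dropout, essentially all Visit 1-discordant people must be discordant again: 0.816 × (0.85/0.93) = 74.6%. Reaching 65% by this route needs about 5.4-fold dropout with all of them discordant again.

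**How few inform an imputation.** Of 56 Visit 1-discordant people, 56 × 0.10 ≈ 6 drop out at the average rate and 56 × 0.263 ≈ 15 at threefold, over both arms.

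**Fragility near the threshold.** Completer results of 306/340 vs 289/340 give z = 1.97. Setting the 38 dropouts in each arm to 85% gives z = 1.85, before any allowance for imputation uncertainty.

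**The case against.** Subtracting expected dropouts in a power calculation is routine and is not an analysis rule. The plan nowhere says that it will analyse completers only, and its intent-to-treat wording sits next to a remark on participants switching arms. A reader might infer a declared completers-only design; the documents do not support that. What stands is narrower: with no rule for missing outcomes, the named model delivers such an analysis by default.

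A reader might also infer that the non-practice arm gets only periodic contact. It does not. Both arms get the contacts two weeks and two days before Visit 2, the home exam meant partly to encourage attendance, and the same $80. The practice arm's extras are the 3-month practice reminders, follow-up calls and possible recall visits. Participants with more than minimal pain at Visit 1 are asked not to practise, so practice reminders have little purpose for them. The contact difference is real but smaller than the two arm descriptions alone suggest.

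Finally, the confounder list is given as examples, already includes city and anxiety, and is followed by a promise to examine the other study data. Visit 1 concordance is therefore not excluded. It is simply not pre-specified.

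**Conclusion.** The gap is real and worth closing: the only primary comparison in Aim 2 has no stated method for about one in ten outcomes. Its likely size is modest. With 5% versus 15% loss, the bias is about 0.5 points under the dropout pattern built from the plan's own Visit 1 discordance estimate, 1.2 points at 75% dropout concordance, and 2.5 points in an extreme case, against a standard error of 2.7. The loss rates, the threefold dropout and the dropout concordance are all assumptions.

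Two stronger readings are tempting. One is that the bias runs against practice. That holds only if the non-practice arm loses more people of lower concordance; the practice arm's added tasks could produce the reverse. The other is that the bias is about half the planned effect. That is the 65% case (2.5 of 4.8 points), and reaching it through Visit 1 discordance requires the implausible conditions shown above.

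**What to change.** 1. Analyse by assigned arm. Include Visit 1 concordance, city and exam type (ASE or ACE) as fixed, pre-specified covariates in the practice model, outside the p≤0.25 screen and backward selection. If loss depends only on arm and these covariates, a correctly specified adjusted model already deals with it.
2. For randomised participants whose Visit 2 concordance is missing, multiply impute from arm and Visit 1 data. Keep the imputation model parsimonious, because few Visit 1-discordant people will drop out. Report dropout by arm and by Visit 1 concordance, add a tipping-point analysis that shifts imputed concordance in both directions, and keep the completer analysis as a sensitivity analysis. Say what is done for anyone without a Visit 1 result, for example after stopping the exam because of pain.
3. State separately how the analysis treats participants not asked to do the Visit 2 exam because of a contraindication, and the 44 non-resolving cases. Their outcome may be undefined rather than missing, so they should not be imputed by default. The 44 also rests on resolution within nine months while Visit 2 is at six; these passages must be reconciled.

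The cost is SAP wording and modest programming. The Visit 1 data are already collected, and no visit or procedure changes. The main downside is reliance on a stated missing-at-random model, which the tipping-point analysis tests.
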